# Introduction

## Purpose

The goal of this study is to evaluate the effectiveness of a brief, intensive 1-day psychotherapy group intervention (Acceptance and Commitment Therapy, ACT), compared to a 12 week time control group on anxiety symptoms, vascular function, inflammation, muscle sympathetic nerve activity (mSNA), and oxidant stress. Individuals who are interested in the study will be identified by an online screening survey and will be contacted by the research team; advertisements, flyers and mass emails will direct individuals to the online screening survey. Those deemed eligible to participate will be randomized to the ACT intervention or the control group. Assessments of anxiety symptoms (via various surveys) and vascular function (via non-invasive, well-established techniques) will be performed at baseline and 12 weeks post-ACT group intervention session. In addition, reassessment of anxiety symptoms via aforementioned surveys will take place 6 weeks post-ACT group session. After 12 weeks, anxiety and vascular assessments will be repeated to re-evaluate severity of anxiety symptoms, vascular function, inflammation, and oxidant stress.

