  - i) Subject will be instrumented with 24-hour ambulatory blood pressure monitor to wear home for 24 hours. Subject will return monitor to research coordinator the following day.
  - j) Subject will receive snack or meal from CRU dining room.
- 3) Visit 3: Group Intervention Workshop
- Subjects randomized to the ACT Intervention group will attend a 1-day group workshop. Each ACT group will be held at the University of Iowa Hospitals and Clinics, include a total of 8-10 subjects, and last ~4-6 hours. At the start of the workshop, participants will be asked to fill out the STAI and PANAS-X questionnaires (hard-copy). The ACT group will be conducted by either 1 or 2 psychologists. Participants will be given a booklet in which two broad areas will be covered:
- a) Behavioral Change training will involve
    - i) teaching subjects how to recognize ineffective patterns of behavior and habits
    - ii) exploring and setting life goals and those related to mental and physical health
    - iii) promoting effective and committed actions to achieve these goals despite the urge to do otherwise
  - b) Mindfulness and Acceptance Training will emphasize new ways of managing troubling thoughts, feelings, and physical sensations (i.e. learning how to recognize, and develop cognitive distances from unhelpful thoughts such as "I can't take this anymore" and learning how to willingly face experiences that cannot be changed). In-session exercises and practice will be heavily emphasized during the group intervention and handouts will be distributed for home use. Lunch will be provided and breaks will be offered to minimize fatigue.
- 4) 6-Week Post Intervention Follow-up:
- Subjects will be contacted via phone and email 6 weeks +/- 10 days after they have completed the ACT intervention group workshop.
- a) Survey Portion
- Subjects will be emailed a link to complete surveys listed below online via REDCap or have the option of completing via phone: State-Trait Anxiety Inventory; Positive and Negative Affect Schedule-Expanded Form; Anxiety Inventory; Depression Inventory; Early Experience Questionnaire; Acceptance and Action Questionnaire II; Committed Action Questionnaire; Short Form Health Survey
- b) Vascular portion of visit:
    - i) Subject will arrive at the CRU between 7-9 am after an overnight 8 hour fast (water encouraged).

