      - (1) Subjects on vasoactive medications will be asked to hold medications on the morning of experimental testing, but will bring medications with them to be taken after the visit.
    - ii) A research staff member will administer Sleep Surveys (including the Berlin Questionnaire, Karolinska Sleep log and the Sleep Quality Assessment [PSQI])
    - iii) A research staff member trained in microneurography will record from the peroneal nerve with a microelectrode for measurement of muscle sympathetic nerve activity (See 'Methods' for details). Subject will be given an mSNA Questionnaire to assess any follow-up discomfort at the sight of microneurography electrode over the next 7 days and mail it back to the study staff in 7 days. Participants will wear two E4

- wristbands (one on each wrist) during the procedure. Measures of brachial artery blood flow using Doppler ultrasound, a mental math test, and a cold pressor test may also be performed during microneurography
- iv) Venous Occlusion Plethysmography (VOP) will be performed (see 'Experimental Methods' for details).
  - v) Subject will receive snack or meal from CRU dining room.
- 5) Visit 4: 2nd Experimental Visit (12-weeks post-intervention)  
All experimental procedures described in Visit 2 will be repeated.
- a) Subject will arrive at the CRU between 7-9 am after an overnight 8 hour fast (water encouraged).
    - i) Subjects on vasoactive medications will be asked to hold medications on the morning of experimental testing, but will bring medications with them to be taken after the visit.
  - b) CRU staff/nurse will obtain urine or serum sample for pregnancy test (women of childbearing age only).
  - c) Prior to experimental testing, the subject will complete (for a 2nd time) the following surveys/questionnaires:
    - i) State-Trait Anxiety Inventory
    - ii) Positive and Negative Affect Schedule-Expanded Form
    - iii) Anxiety Inventory
    - iv) Depression Inventory
    - v) Early Experience Questionnaire
    - vi) Acceptance and Action Questionnaire II
    - vii) Committed Action Questionnaire
    - viii) Short Form Health Survey
    - ix) Sleep Surveys (including the Berlin Questionnaire, Karolinska Sleep log and the Sleep Quality Assessment [PSQI])

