### Control Group

If randomized to the 12-week time control group, study procedures are the same as the Intervention Group with the exception of Visit 3, the Group Intervention Workshop. However, the control subjects will be emailed to complete the STAI and PANAS-X surveys prior to the ACT Group Workshop Date. The surveys will be completed online via REDCap (with individualized link as indicated).

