### Primary Endpoint Analysis

Changes in our primary outcome of interest, anxiety as measured by the Beck anxiety inventory (BAI), will be assessed using a linear mixed effect model with intervention group as the fixed effect between-subjects factor of interest and repeated measurements (baseline, 6 weeks, 12 weeks) within-subjects of the anxiety inventory as the primary dependent variable. Individual participants will be initially modeled as a random effect including both an intercept term and, if necessary, slope. The random effect for slope will be removed for an intercept only model if the random slope does not substantively improve the model or if there are issues with model fitting. Fixed effects covariates for any sociodemographic or clinical variables that differ between groups despite randomization can be added.

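### Follow-up is timed from completing the ACT workshop, so ACT non-attenders have no defined 6- or 12-week time point, and the controls' clock is implied but not stated

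*Combined protocol and SAP*

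**What the plan says.** Under Assessment Schedule, Intervention Group, item 4, the 6-week follow-up is triggered by completion of the workshop: "Subjects will be contacted via phone and email 6 weeks +/- 10 days after they have completed the ACT intervention group workshop". The survey portion of that contact includes the Anxiety Inventory. Item 5 sets the last assessment as "Visit 4: 2nd Experimental Visit (12-weeks post-intervention", with no window.

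The Purpose section uses slightly different wording. It says that anxiety and vascular assessments "will be performed at baseline and 12 weeks post-ACT group intervention session", and that "reassessment of anxiety symptoms via aforementioned surveys will take place 6 weeks post-ACT group session".

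For controls, the Control Group section says that "study procedures are the same as the Intervention Group with the exception of Visit 3, the Group Intervention Workshop". The only date it gives them concerns two other questionnaires: "the control subjects will be emailed to complete the STAI and PANAS-X surveys prior to the ACT Group Workshop Date". The Beck inventory is not one of these.

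Under Primary Endpoint Analysis, "anxiety as measured by the Beck anxiety inventory (BAI), will be assessed using a linear mixed effect model", with intervention group as the between-subject factor and "repeated measurements (baseline, 6 weeks, 12 weeks) within-subjects of the anxiety inventory as the primary dependent variable". The statistical sections define no analysis population and give no rule for ACT participants who do not attend.

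**The concern.** Completing the workshop happens after randomisation and is possible in one arm only. A coordinator who applies item 4 as written to an ACT participant who missed the day has no date from which to count six weeks. The same difficulty arises at 12 weeks if post-intervention is taken to mean after receiving the intervention. A control cannot miss a workshop, so nothing comparable removes controls from follow-up.

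If non-attenders drop out of follow-up for this reason, the model compares those who came with everyone assigned to control. Attendance may be related to how anxiety would have evolved anyway. The mixed model uses each person's baseline score, so selection on baseline severity is largely dealt with under missing-at-random. It cannot correct differences beyond baseline, and it treats ACT non-attenders as if they had responded like attenders with the same baseline. Follow-up that was never collected cannot be recovered at the analysis stage.

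The control clock is a second, smaller gap. The completion rule cannot be applied to people who have no workshop. If sites started controls from Visit 2 and ACT participants from the workshop, the arms could differ in time since baseline.

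**Working it through.** **1. The plan's own figure.** Inputs from Sample Size: m = 3 assessments, within-person correlation 0.4, effect 0.5 SD, 80% power, alpha 0.05 (taken as two-sided).

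- n per group = 2(1.960 + 0.842)² × [1 + (3 - 1) × 0.4] / (3 × 0.5²) = 37.67, rounded up to 38.
- With 10% dropout: 38/0.9 = 42.2, rounded up to 43.

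Both stated figures reproduce. The point concerns timing and follow-up, not the sample size.

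**2. The passages side by side.**

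| Participant | 6-week anchor | 12-week anchor |
|---|---|---|
| ACT, attended | Date the workshop was completed | Same, as post-intervention |
| ACT, did not attend | Not defined in item 4; Purpose could be read as the session date | Not defined; same possible reading of Purpose |
| Control | Not stated; workshop date implied through STAI and PANAS-X | Not stated; same implication |

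**3. Illustration of size.** The documents supply only the 0.5 SD, and they give it as the between-group difference to detect. Everything else here is assumed:

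- a fraction p of the ACT arm does not attend, gets no benefit and is lost to follow-up;
- attenders gain 0.5 SD;
- without treatment and given baseline, non-attenders would do d SD worse than attenders (a negative d means better).

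Then:

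- As-assigned effect = (1 - p) × 0.5.
- Controls include would-be non-attenders, so their mean lies p × d below that of untreated attenders. The attenders-only estimate is therefore 0.5 + p × d.
- Departure = (0.5 + p × d) - (1 - p) × 0.5 = p × (0.5 + d).
- With no true effect, the bias is p × d.

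| p | d | Departure, 0.5 SD effect in attenders | Bias, no true effect |
|---|---|---|---|
| 10% | -0.5 | 0 | -0.05 |
| 10% | 0 | 0.05 | 0 |
| 10% | +0.5 | 0.10 | +0.05 |
| 20% | -0.5 | 0 | -0.10 |
| 20% | 0 | 0.10 | 0 |
| 20% | +0.5 | 0.20 | +0.10 |

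**4. Power if non-attenders are followed and counted.** By the plan's formula the SD of a person's average is √(1.8/3) = 0.775, and power = Φ(effect / [0.775 × √(1/n₁ + 1/n₂)] - 1.96). Enrolling 150 at 2:1 gives 100 and 50, or 90 and 45 after 10% dropout.

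| Assumed non-attendance | As-assigned effect (SD) | Power, 38 and 38 | Power, 90 and 45 |
|---|---|---|---|
| 0% | 0.50 | 80% | 94% |
| 10% | 0.45 | 72% | 89% |
| 20% | 0.40 | 61% | 81% |
| 30% | 0.35 | 50% | 70% |

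**The case against.** The strongest reply is that silence should not be turned into a rule. A reader might infer that non-attenders' anxiety scores will not be collected. The documents do not say so. The completion wording governs only the 6-week contact, the Purpose section refers to the group session, which can be read as a calendar date, and the primary model is not limited to attenders. That stands: the time point is undefined, and follow-up is not excluded. What remains is that the operational text staff would follow is the completion rule, and nothing elsewhere overrides it.

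A reader might also infer that controls have no time zero at all, or that the arms will certainly have different intervals from baseline. The Control Group section ties controls to a workshop date for two surveys and otherwise gives them the same procedures, so that anchor is implied. A wait for groups of 8-10 to fill is a plausible inference, but the documents do not describe one. The gap is that the implied anchor is not written down for the 6- and 12-week assessments, and nothing says which workshop a control belongs to.

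Finally, one might conclude that the plan necessarily overstates the effect of ACT. It does not follow. The non-attendance rate and the attender difference are both unknown, and less anxious people might equally skip the day. At d = 0 the whole departure is the gap between an effect in attenders and an effect of assignment, with no selection bias. People who leave early may also get some benefit, which the illustration ignores.

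**Conclusion.** The point holds as a gap in definition with a real route to bias. Taken literally, the schedule makes follow-up in the ACT arm depend on a post-randomisation event. It leaves the controls' start date to inference, and no statement of analysis as randomised protects the comparison.

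The consequence arises only if non-attenders are in fact lost. In that case, under the assumptions above, the estimate exceeds the as-assigned effect by 0 to 0.20 SD for 10%-20% non-attendance, that is, up to 40% of the 0.5 SD target (0.20/0.5). Where there is no true effect, the bias lies between -0.10 and +0.10 SD. These are illustrations, not predictions. The stated sample sizes of 38 and 43 per group are unaffected.

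**What to change.** In items 4 and 5 of the Intervention Group schedule and in the Control Group section, time the 6- and 12-week assessments in both arms from one date that does not depend on attendance. Two choices would serve: the scheduled workshop date to which each participant, including each control, is linked at randomisation; or the randomisation date. Align the Purpose section with the choice. State that all randomised participants are contacted at those times whether or not they attended, and record attendance as full, partial or none. Under Primary Endpoint Analysis, state that all randomised participants are analysed in their assigned group.

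The surveys already go out by link or telephone, so reaching non-attenders needs little new machinery for the primary outcome. There are three costs. If the workshop date is the anchor, each control must be linked to a workshop, which the Randomization section does not currently provide for. A participant moved to a later workshop would be assessed sooner after treatment, so the actual date should be recorded. And the estimated effect may be smaller because non-attenders count. On the planned 2:1 enrolment, power would still be about 81% at an assumed 20% non-attendance, falling to about 70% at 30%.

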### Control Group

If randomized to the 12-week time control group, study procedures are the same as the Intervention Group with the exception of Visit 3, the Group Intervention Workshop. However, the control subjects will be emailed to complete the STAI and PANAS-X surveys prior to the ACT Group Workshop Date. The surveys will be completed online via REDCap (with individualized link as indicated).

## Safety Assessment

### Physical Risks

- Fasting 8 hours: The most common risk when fasting is dehydration, therefore the subject will be encouraged to drink plenty of water. Subjects may experience hunger and irritability and if they experience fainting, nausea, or vomiting they will be instructed to stop fasting.
- Blood Sample: Potential risks associated with obtaining blood samples are minimal but include slight bruising, pain, a temporary feeling of faintness, and/or a small risk of infection. All blood draws will be performed by CRU staff, nurse or research team member trained and certified in drawing blood. There are no known risks associated with urine collection.
- Endothelial Cell Collection: The risks related to the venous endothelial cell collection do not appear to be any greater than those associated with the placement of an intravenous catheter into antecubital vein. In the Co-Investigator's experience ([name]) with this technique at the University of Colorado Clinical and Translational Research Center, there were no adverse events encountered in >150 of these procedures performed between 2005-2009 in young, middle-aged and older healthy adults.
- Venous Occlusion Plethysmography (VOP): There are no known risks associated with the strain gauge device or with temporary changes in blood flow using a blood pressure cuff. Minor discomfort in the forearm and/or hand may occur when the blood pressure cuffs are inflated. This feeling is completely reversed within several minutes after the cuff is released with no permanent discomfort.
- Pulse Wave Analysis: There are no known or foreseeable risks associated with the use of applanation tonometry for pulse wave analysis. ECG electrodes may cause minor irritation to the skin.
- Carotid Artery Compliance: There are no known or foreseeable risks associated with the use of carotid echocardiography. ECG electrodes may cause minor irritation to the skin.
- Non-invasive Blood Pressure Monitoring: There are no known risks associated with the use of a small cuff on your finger to monitor small changes in blood pressure.

- Antihypertensive Medication Withdrawal: There is an increase in cardiovascular diseases such as strokes, heart failure, aortic aneurysms, and pulmonary embolism when these medications are stopped for longer periods of time than in this study. Subjects will be asked to bring medications with them to experimental Visits 2 and 4 to resume medication use once experimental testing is complete. We do encourage subjects to discuss holding medication dosages with their personal physician before doing so.
- Retinal Vascular Measurements: Since the subjects may be dilated with 0.5% tropicamide and there can be a risk in patients with angle closure glaucoma if they have not had a procedure to correct this. Patients at the UIHC eye clinic usually have a corrective procedure done as a preventative measure. If there is a question about angle closure glaucoma, we will do a slit lamp exam to rule this out before proceeding. Dilating drops may also cause an initial burning or stinging sensation that goes away after installation. There is a small risk of sensitivity or an allergic reaction that would cause redness or irritation. The dilating drops will temporarily affect close vision (reading distance) for 2 to 6 hours, if they do not normally use a reading correction. Some people may be uncomfortable driving during this time. Also, the sun and bright lights may cause some discomfort, but sun shades are provided if desired. Occasional temporary stinging, burning and conjunctival redness may occur with the use of 0.5% proparacaine.
- Microneurography: Direct recording of nerve activity (microneurography) has a very small degree of risk. Over 2,000 microneurographic studies have been performed in our laboratories at the University of Iowa since 1984. There have been no significant complications. Approximately 7% of subjects experience minor tingling in the leg, foot or arm for a few days after the study, but these symptoms have been transient. In the mental math test, the subject may become frustrated and in the cold pressor test, the subject may feel uncomfortable, however there are no known physical risks associated with these tests. The subject may experience discomfort at the site of microneurography following the study visit, and discomfort becomes more likely if they engage in high-intensity exercise with their legs (e.g. leg press, running, cycling, etc.), particularly within 24 hours of the procedure. In addition to this information being in the consent, study staff will verbally remind the subject before and after the procedure at the visit. If a subject does return the microneurography questionnaire indicating they have symptoms the study staff will call the participant and offer a physical exam by [name].
- 24-hour Ambulatory Blood Pressure: Participants may experience abrasions, petechiae, or bruising from the pressure exerted when the cuff inflates, particularly if s/he is taking anticoagulants. Cuff inflation may cause mild discomfort and/or may be disruptive to sleep.
- Fatigue may set in during the 6 hour group workshop.

#### Minimizing Risks

- All IV insertion, blood draws, and microneurography techniques will be performed by CRU staff, nurse or trained research team member.
- During experimental testing (VOP) the subject will relay any discomfort to research staff and will be reminded they can elect to stop testing if discomfort becomes intolerable.
- Answers to questionnaires are confidential and the participant is able to skip any question they are not comfortable answering. To ensure confidentiality, a study number assigned at the beginning of the study will identify materials containing patient information. All study materials and consent forms will be kept in locked files stored in an office that will

also be locked. Confidentiality among subjects will also be emphasized at the group workshop.

- Some questions on the various health surveys or questionnaires may include questions about depressed mood or thoughts of suicide. To address this risk, we will provide the following information to all individuals who complete the online pre-screen:

"Thank you for completing our survey, which included questions about depression and anxiety. If you are struggling with anxiety or depression, we encourage you to seek help. \*Important note: The information below is provided as a courtesy and is NOT related to your responses on the screening survey you just completed.

+If you are a student, the University of Iowa offers confidential and professional mental health services through the University Counseling Services.

-University Counseling Service

[contact] or e-mail [[contact]](mailto:[contact])

+If you are an employee, The University of Iowa offers services through the Employee Assistance program. We have provided the contact information for these and other mental health services available in the area.

-University of Iowa Employee Assistance Program (EAP):

[contact] or email [[contact]](mailto:[contact])

+Other Resources:

-Mental Health Services Locator Website in Iowa:

Go to <http://store.samhsa.gov/mhlocator>, and click on Iowa on the map.

-Suicide Hotline:

Website: <http://suicidehotlines.com>

[name]

[name]

Both hot lines offer immediate suicidal crisis counseling and information about crisis centers in your area as well as referrals to mental health centers in your area.

-2-1-1 Infoline:

Information, referral and crisis intervention service for the State of Iowa. Operates 24 hours a day. Can be reached by dialing 2-1-1 in IA."

- Once the subject is enrolled in the study, if these or other questions on other health forms or during the MINI lead to a concern for the participant's safety or the safety of others, the PI will be notified immediately and will perform a risk assessment. The participant will be kept informed of the need for additional evaluation and will be encouraged to ask questions. If the participant is deemed a safety risk by the PI, the participant's primary psychiatrist will be notified. If the participant does not have a primary psychiatrist or if the primary psychiatrist cannot be contacted, we will arrange for an evaluation in the UIHC Emergency Room or Adult Psychiatry Clinic.
- Regular breaks are given during the workshop to reduce fatigue.
- Retinal Vascular Measurements: Patients at risk for angle closure glaucoma who are seen at the UIHC eye clinic routinely have a corrective procedure done to prevent episodes of high intraocular pressure (high IOP) that can result when dilated. If there is a question about angle closure glaucoma, we will do a slit lamp exam to rule this out before proceeding. We will tell subjects before we put the drops in that they may cause a stinging or burning sensation that will go away. We will ask subjects if they have had a reaction to dilating drops in the past. Side effects of the tropicamide drops resolve after

discontinuation of the drops. We will ask subjects if they have had any prior reaction to proparacaine. The burning or redness usually subside in a few minutes. All eye drops used in the study are routine eye drops used in the eye clinic at UIHCS. We will provide subjects with disposable sunglasses to add additional comfort from the light.

